### 6.3. Measures to Minimize Bias: Randomization and Blinding

Not applicable as this is an open-label study.

### **6.4.** Study Treatment Compliance

Compliance with all study-related treatments must be emphasized to the participant by the site personnel, and appropriate steps should be taken to optimize compliance during the study.

Compliance with ruxolitinib cream will be evaluated by participants' adherence to the application regimen and drug accountability documented by the site staff and monitored by the sponsor/designee.

In general, the application compliance will be determined by the number of actual versus anticipated number of applications, which should be within 70% to 130% of the prescribed number of applications. Participants will be instructed to bring all tubes of study cream with them to the study visits in order for site personnel to conduct tube counts to assess study cream accountability. The drug accountability documentation will be used by the sponsor to calculate treatment compliance.

Compliance with NB-UVB will be determined by the number of sessions as recorded by the NB-UVB machine. Participants will be instructed to bring the session recording device with them to the study visits in order for site personnel to conduct the compliance assessment. Site staff must provide source documentation of all treatment dates and details.

#### 6.5. Dose Modifications

#### 6.5.1. Criteria and Procedures for Application Interruptions of Study Cream

Safety concerns should be discussed with the sponsor immediately upon occurrence or awareness to determine whether the participant should continue or discontinue application of study cream.

In some circumstances, it may be necessary to temporarily interrupt application of ruxolitinib cream. Except in cases of emergency, it is recommended that any findings of concern (eg, AE) be confirmed and that the investigator consult with the sponsor medical monitor (or other representative of the sponsor) before interrupting study cream. Additionally, the investigator must obtain approval from the sponsor before restarting study cream. Participants who have a recurrence of the initial AEs upon restarting the study cream and the AE is confirmed related to the study cream may need the study cream to be permanently discontinued.

If a participant has an AE at an application site, application of ruxolitinib cream to that site can be temporarily interrupted without interrupting application of study cream elsewhere.

Instructions for application interruptions for ruxolitinib cream are outlined in Table 8. Individual decisions regarding interruptions should be made using clinical judgment in consultation with the medical monitor (whenever possible), taking into account relatedness of the AE to the study cream and the participant's underlying condition.

If it is unclear whether a skin reaction is related to ruxolitinib cream or the NB-UVB, the investigator should consider interrupting both.

Table 8: Guidelines for Interruption and Restarting of Study Cream

Adverse Event	Action Taken
Chemistry	
ALT (> $3 \times ULN$ ) or AST (> $3 \times ULN$ )	• Laboratory abnormalities should be confirmed with repeat testing within 48 hours whenever possible and immediate delivery of the laboratory results requested.
	• Study cream applications must be interrupted. At the discretion of the investigator, after consultation with the sponsor, study cream application may be restored once these have resolved.
Other laboratory abnormalities	
Any other Grade 3 or higher laboratory abnormality	• Laboratory abnormalities should be confirmed with repeat testing within 48 hours whenever possible and immediate delivery of the laboratory results requested.
	• Study cream applications must be interrupted. At the discretion of the investigator, after consultation with the sponsor, study cream application may be restored once these have resolved.
Any Grade 4 laboratory abnormality or AST or ALT (> 5 × ULN)	• Laboratory abnormalities should be confirmed with repeat testing within 48 hours whenever possible and immediate delivery of the laboratory results requested.
	Discontinue study cream if lab abnormalities are confirmed.

# 6.5.2. Criteria for Permanent Discontinuation of Study Cream Due to an Adverse Event

The occurrence of unacceptable severity of an AE that is related to study cream application will require that the study cream be permanently discontinued. Unacceptable severity is defined as follows:

- Occurrence of an AE that is related to treatment with the study cream that, in the judgment of the investigator or the sponsor's medical monitor, compromises the participant's ability to continue study-specific procedures or continuing treatment is considered not to be in the participant's best interest.
- Worsening of vitiligo that requires treatment with a prohibited concomitant medication.

See Section 7 for discontinuation procedures.

#### 6.5.3. Dose Modification for NB-UVB

On subsequent treatments, the NB-UVB machine will record participant responses about pinkness/tenderness of the skin during the previous days. Table 9 shows the dose modifications that should occur based on skin reaction. These dose modifications will be programmed into the machine. If there is severe pinkness/redness or there is pain, the participant may need to have an unscheduled visit for the investigator to evaluate the participant. The participant is not to

undergo any further light treatments until it resolves, and treatment can restart at a 15% decreased dose. Once the ordered holding dose is reached, hold at that dose until evaluated by the investigator. The holding dose may be increased at that time.

If it is unclear whether a skin reaction is related to ruxolitinib cream or the NB-UVB, the investigator should consider interrupting both.

If the participant has missed NB-UVB treatments, dose adjustments for missed treatments are listed in Table 10.

Table 9: NB-UVB Dose Adjustments Based on the Skin Assessments

Responses to NB-UVB Machine Question a	Skin Assessment	Dose Adjustment
No, or < 24 hours	No erythema reported after last treatment	Increase by 10%
24 – 48 hours	Mild erythema but not painful	Hold dose constant
> 48 hours	Moderate erythema or painful	Decrease by 10%
Still red/pain	Severe, painful erythema	Wait until resolution, decrease dose by 15%

<sup>a The NB-UVB machine will provide the following question to the participant, "Were you in pain or red after your last treatment?". The participant's response will result in a hold or change to the dose as noted in the dose adjustment column.

**Table 10:** NB-UVB Dose Adjustments for Missed Treatments

Length of Time Since Previous Dose	Dose Adjustment
Up to 1 week	Maintain dose
1-2 weeks	Decrease by 25% to a minimum of 200 mJ/cm 
2-3 weeks	Decrease by 50% to a minimum of 200 mJ/cm 
3-4 weeks	Decrease by 75% to a minimum of 200 mJ/cm 
> 4 weeks	Restart at 200 mJ/cm 

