Application instructions:	A thin film is applied BID to depigmented vitiligo areas.
Packaging and labeling:	Ruxolitinib cream will be provided in 60 g tubes. Each tube will be labeled as required per country requirement.
Storage:	Ambient (15°C-30°C/59°F-86°F)
Status of treatment in participating countries:	Investigational

**Table 7:** Study Treatment Information (NB-UVB)

Study treatment name:	NB-UVB (311-312 nm)
Dosage formulation:	Cleared medical device
Dosage levels:	Starting dose = 200 mJ/cm  Increase dose by 10% at each visit until mild erythema lasting < 24 hours as reported by the participant. Hold dose at 1500 mJ/cm  – this may vary or be increased over the course of treatment. Dose information will be collected in the database.
Administration instructions:	Three times a week; not on consecutive days.
Status of treatment in participating countries:	Standard of care

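### The home NB-UVB device is programmed to add 10% after a reaction of under 24 hours, where Table 7 ends the increases, and as described it does not distinguish pain that has cleared from redness

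*Protocol*

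**What the plan says.** Protocol Section 6.1, Table 7, starts NB-UVB at 200 mJ/cm² and gives the escalation rule: "Increase dose by 10% at each visit until mild erythema lasting < 24 hours as reported by the participant". The default holding dose is 1500 mJ/cm², which may vary or be raised. Group A participants treat themselves at home with a sponsor-supplied machine (Section 4.1).

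Section 6.5.3 then sets adjustments by skin reaction in Table 9 and says of them: "These dose modifications will be programmed into the machine". The table's footnote gives one prompt, "Were you in pain or red after your last treatment", and says that the response determines the hold or change. The four rows are:

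| Participant's answer | Row label | Programmed step |
|---|---|---|
| "No, or < 24 hours" | "No erythema reported after last treatment" | plus 10% |
| 24 to 48 hours | "Mild erythema but not painful" | hold |
| over 48 hours | "Moderate erythema or painful" | minus 10% |
| still red or in pain | severe and painful | wait until resolved, then minus 15% |

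The text of Section 6.5.3 adds a rule for severe redness or for pain: an unscheduled visit may be needed, no light is given until resolution, and treatment can restart 15% lower. The SAP has no rule on NB-UVB dose. It covers only session compliance (SAP Section 6.6).

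**The concern.** The same participant report leads to different actions in two tables of one protocol. In Table 7, brief mild erythema is the signal that ends the increases. In Table 9 it earns another increase, in a row whose label says that there was no erythema at all. A site trained on Table 7 would expect one dose, and the device would deliver another.

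Pain raises a separate problem. Two row labels in Table 9 imply that pain has been considered, since row 2 is for reactions without it and row 3 for reactions with it. Yet as described, the device learns only whether there was pain or redness, and for how long. Pain that has gone by the next session is therefore handled by its duration, whatever the label says.

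What is at stake is the dose given in unsupervised home treatment, in participants as young as 12 (Section 5.1). Safety and tolerability of the combination is a secondary objective. A participant who answers truthfully after a short painful reaction can be given a higher dose at the next session.

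**Working it through.** The plan states no figure on this point to reproduce. The check sets the rules side by side and works out the dose multiplier for each answer. Write d for the dose at the session that caused the reaction. Table 7 speaks of increases at each visit. Because treatment is three times a week at home, that is read here as each session.

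**1. The under-24-hours answer.**
- Table 7: the stopping point has been reached, so no increase: 1.00 × d.
- Table 9, row 1: 1.10 × d.
- Ratio: 1.10 / 1.00 = 1.10.

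The full step applies while 1.10 × d ≤ 1500, that is, for d up to 1500 / 1.10 = 1364 mJ/cm². For assumed values of d:

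| d (assumed, mJ/cm²) | Table 7 | Table 9 |
|---|---|---|
| 400 | 400 | 440 |
| 600 | 600 | 660 |
| 800 | 800 | 880 |
| 1400 | 1400 | 1500 (capped; ratio 1.07) |

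**2. Whether the holding dose limits this early on.** Going from 200 to 1500 in 10% steps takes ln(1500/200) / ln(1.1) = 21.1 steps. The default cap therefore first limits a step at the 22nd increase. At three sessions a week that is 22 / 3 = 7.3 weeks after the start, if no session is held or reduced. Before then the cap gives no protection against a single step.

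**3. Pain that has cleared before the next session.** Three rules could apply: the duration answer, the painful label in row 3, and the pain rule in the text of Section 6.5.3 if it is read to cover pain that has resolved.

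| Pain lasted | Programmed by duration | Row 3 painful label | 6.5.3 text | Programmed ÷ label | Programmed ÷ text |
|---|---|---|---|---|---|
| under 24 h | 1.10 d | 0.90 d | 0.85 d | 1.22 | 1.29 |
| 24 to 48 h | 1.00 d | 0.90 d | 0.85 d | 1.11 | 1.18 |

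The 24-to-48-hours answer also places a painful reaction in a row labelled as not painful.

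**4. Pain still present at the next session.** Row 4 and the text agree: wait for resolution, then 0.85 × d. There is no conflict here.

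**5. Safeguards.** Section 9.10 tells a participant with skin burning to use emollients and contact the site for instructions. Section 6.5.3 allows for an unscheduled visit, stops light until pain resolves, and has the investigator review the holding dose. Section 6.4 has the session recorder brought to visits. None of these is tied to the under-24-hours or the 24-to-48-hours answer. Scheduled visits after Week 12 are at Week 16 and then every 8 weeks (Table 4), so earlier correction depends on the participant reporting the reaction.

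**The case against.** The strongest reply on the first part is that the delivered rule is not in doubt: Table 9 is programmed, and Table 7 is a summary. Table 7 states a hold only at 1500 and otherwise just says when increases end. Nothing in the documents shows that Table 7 is the intended limit and Table 9 the slip. This stands as far as it goes. Which way to align the tables is a clinical choice. It does not reconcile them, and the row 1 label is wrong on either choice, because an under-24-hours answer to that prompt reports a reaction.

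On the second part, the footnote prompt is a yes/no question while the answers are durations, so the device must show at least one prompt or menu that the protocol does not describe. The text also says that the machine records tenderness. Pain may therefore be captured separately. This stands as a limit on what can be concluded from the protocol.

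The pain rule in Section 6.5.3 is not expressly confined to pain still present at the next session. Read broadly, it is a safeguard for cleared pain too. On that reading, though, the programmed plus 10% or hold departs further from the text.

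A reader might go on to infer more than the documents support:

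- That the excess compounds over successive sessions. This needs an unbroken run of under-24-hours answers while the dose rises. Nothing supports such a run, and rows 2 to 4 hold, reduce or stop the dose once reactions last longer.
- That row 3 is nearly out of reach, since sessions are "Three times a week; not on consecutive days" and many gaps are about two days. That shows no harm. A reaction still present at 48 hours goes to row 4, which is stricter than row 3.
- That everyone on NB-UVB is affected. The documents give no rate of brief or painful erythema, so neither participants nor sessions affected can be counted.

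**Conclusion.** The concern holds as an inconsistency in the dosing rules that bears on safety. Table 9, as programmed, increases the dose on the report at which Table 7 ends the increases. The dose after that answer is 1.10 times what Table 7 allows, below the holding dose. As the prompt is described, pain that cleared within 24 hours gives plus 10% and pain that cleared in 24 to 48 hours gives a hold. Both conflict with Table 9's own painful label (minus 10%). If Section 6.5.3 covers cleared pain, both also conflict with its restart at minus 15%.

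This rests on two assumptions: that a visit in Table 7 means a treatment session, and, for the pain part only, that the device has no further prompt separating pain from redness. The size is per answer, and the frequency cannot be estimated. No statistical result is affected. The point should still be settled, because following Table 9 as written breaks another stated rule of the protocol.

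**What to change.** 1. In Table 9, separate the no-reaction answer from the under-24-hours answer. Keep plus 10% for no reaction, make the under-24-hours action agree with Table 7 (no increase), and correct the row 1 label. If the sponsor's clinical lead intends Table 9's rule for painless brief erythema, amend the Table 7 stopping point instead.
2. State that any pain since the last session, including pain that has cleared, means no dose increase and follows the Section 6.5.3 pain rule. The clinical lead sets the size of any reduction.
3. Implement this with a separate yes/no pain item on the device. If the device cannot be changed, give participants a written instruction not to treat and to call the site after any painful reaction.

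The cost is wording in Tables 7 and 9 and Section 6.5.3, one reprogrammed answer if Table 7 is kept, and one added prompt or instruction. Escalation would be slightly slower in some participants with pain or brief erythema.

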## 9.10. Treatment of Overdose

There has been no clinical experience with overdose of ruxolitinib cream. Treatment of overdose should consist of general supportive measures.

NB-UVB can result in skin burning similar to sunlight. If the participant experiences skin burning from the NB-UVB device, they should apply emollients and contact the study site for instructions on how to treat the skin reaction.

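### A participant who reacts to NB-UVB at 200 mJ/cm² or below and then has a gap of more than 4 weeks is restarted at, or above, the dose that caused the reaction

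*Protocol*

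**What the plan says.** Table 7 (Protocol section 6.1) sets "Starting dose = 200" mJ/cm² with 10% increases, three sessions a week. Section 4.1 says that the machines are for home use.

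Section 6.5.3 has two adjustment tables.

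- **Table 9** adjusts for skin reactions. The dose is cut by 10% after moderate or painful erythema lasting over 48 hours. After severe painful erythema the instruction is "Wait until resolution, decrease dose by 15" percent. No minimum dose is given. The machine asks about the previous treatment at the next session, and "These dose modifications will be programmed into the machine".
- **Table 10** adjusts for gaps: "If the participant has missed NB-UVB treatments, dose adjustments for missed treatments are listed in Table 10". Its rows are indexed by "Length of Time Since Previous Dose". Up to 1 week, the dose is maintained. For 1-2 weeks the rule is "Decrease by 25% to a minimum of 200" mJ/cm², and the next two rows cut by 50% and 75% with the same floor. Over 4 weeks it is "Restart at 200" mJ/cm², with no reference to the last dose.

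The 200 mJ/cm² floor appears only in Table 10. The section does not say how the two tables combine when both apply.

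**The concern.** Restarting at the starting dose after a long gap is cautious for nearly everyone. It is not cautious for a participant whose own record shows a reaction at that dose. Table 9 has lowered that person's dose because 200 mJ/cm², or something lower, was not tolerated. The last row of Table 10 then undoes the reduction.

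For that participant the table also runs backwards: its shorter gaps hold or lower the dose, and its longest gap raises it above what Table 9 would give. At stake is a repeat skin reaction from a home device in someone already known to react. Nothing in the efficacy analysis depends on it.

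**Working it through.** The plan states no resulting dose for this situation, so there is no figure to reproduce. The check follows the tables.

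**Inputs.** Start 200 mJ/cm² and 10% steps (Table 7); factors 0.90 and 0.85 after a reaction (Table 9); fixed 200 after more than 4 weeks (Table 10).

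**Formulas.** Dose due under Table 9 = d × 0.90 or d × 0.85, where d is the last delivered dose, the one that provoked the reaction. Restart relative to the last delivered dose = 200/d − 1. The last delivered dose is the right comparator because Table 9's question is asked at the next session. If the gap follows the reaction directly, the reduced dose was never given.

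| Reactions before the gap | Last delivered dose d | Due under Table 9 | Table 10 restart | 200/d − 1 |
|---|---|---|---|---|
| One, at 200 | 200 | 180 or 170 | 200 | 0% |
| Two, at 200 then 180 | 180 | 162 or 153 | 200 | +11.1% |
| Two, at 200 then 170 | 170 | 153 or 144.5 | 200 | +17.6% |
| One, at 220 | 220 | 198 or 187 | 200 | −9.1% |
| Two, at 242 then 217.8 | 217.8 | 196.0 or 185.1 | 200 | −8.2% |
| Two, at 242 then 205.7 | 205.7 | 185.1 or 174.8 | 200 | −2.8% |

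The first three rows are the problem: the restart equals or exceeds the provoking dose. In the last three, 200 is below every dose that led to a cut. A participant cut from 220 who reacts again at 198 or 187 has then reacted below 200, and the restart is 200/198 − 1 = +1.0% or 200/187 − 1 = +7.0%.

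**The 1-4 week rows.** Take a last dose of 170 and a 1-2 week gap: 170 × 0.75 = 127.5, below the floor. On the ordinary reading, a decrease that may not go below 200 leaves 170 unchanged. Only a literal reading of the floor lifts it to 200.

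**Doses of 200 or more.** No row raises the dose. For example, 800 becomes 600, 400, 200 and 200 as the gap lengthens.

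**Room for the event.** Planned sessions are 36 × 3 = 108. A 4-week gap is about 4 × 3 = 12 of them, or 11%. If the 21.2% Week 12 T-VASI25 rate quoted in Protocol section 2.4 held here, about 50 × (1 − 0.212) = 39 participants would receive NB-UVB. The affected group is some unknown part of these.

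**The case against.** The case for leaving the text alone has four parts.

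1. **The window is narrow.** The participant must react at 200 or below and begin a gap of over 4 weeks before climbing back. If the reduced dose was given and tolerated, Table 9 itself raises it by 10%: 180 becomes 198 and 170 becomes 187. The restart then exceeds the next routine dose by only 1.0% or 7.0%. This stands, and it keeps the point at low priority.
2. **A wait for a severe reaction to resolve may not be a missed treatment.** It has its own rule, a 15% reduction, and that is the more natural one to apply. This is a fair reading, so the two tables are not in demonstrated conflict. But Table 10's column heading counts time since the last dose, the wait has no time limit, and an ordinary absence after a reaction falls under Table 10 on any reading.
3. **There is oversight.** A gap that starts soon after Week 12 would normally span the Week 16 visit, which Appendix C requires in person and at which session records are reviewed. A painful reaction may prompt an unscheduled visit. After skin burning, section 9.10 has the participant "contact the study site for instructions on how to treat the skin reaction". These lower the risk, but none of them changes or caps the restart dose.
4. **The device may already prevent it.** If the machine cannot go below 200, the case does not arise. The documents state no such limit.

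A reader might go further and compare 200 with the dose due under Table 9, which gives rises of up to 200/144.5 − 1 = 38.4%. The documents do not support that as a rise in delivered dose for these paths: 144.5 is what falls due after a reaction at 170, and against the 170 actually given the restart is 17.6% higher.

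**Conclusion.** The point holds, as an optional clarification. For a participant whose reaction occurred at 200 mJ/cm² or below, Table 10's last row restarts treatment at the provoking dose (one reaction, at 200) or 11.1% to 17.6% above it (a second reaction, at 180 or 170). These figures cover the one- and two-reaction paths that begin at 200 and are not an upper bound for longer runs of reactions.

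This rests on three assumptions: Table 9 can take the dose below 200, since no floor is written; the gap counts under Table 10; and the participant has not re-escalated first. The documents give no rate, and the group is probably small.

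Three wider inferences are not supported. Reactions at 220 or 242 are not a safety concern here, because 200 is below the provoking dose. The 1-4 week rows do not raise a dose on their ordinary reading. Nothing suggests an effect on the Week 48 T-VASI endpoint or its analysis.

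**What to change.** Make two small changes to Table 10.

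- **Row for gaps over 4 weeks:** *Restart at 200 mJ/cm², or at the last dose after any Table 9 reduction if that is lower.* A reduction that falls due on return should count.
- **Footnote to the 1-4 week rows:** *A dose already below 200 mJ/cm² is not raised.* Keep the existing floor in those rows, because it is needed for participants at higher doses.

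Do not add a general rule that the lower of the two tables' doses applies. The row for gaps of up to 1 week maintains the dose and, read by its column heading, covers every routine session. Such a rule could block all escalation.

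With the cap, the problem paths restart at 180, 170, 162, 153 or 144.5. A participant cut from 220 would restart at 198 or 187. Reaction-free 10% increases needed to regain at least 200:

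- from 198 or 187: 1 (217.8; 205.7)
- from 180 or 170: 2 (198, 217.8; 187, 205.7)
- from 162 or 153: 3 (178.2, 196.0, 215.6; 168.3, 185.1, 203.6)
- from 144.5: 4 (159.0, 174.8, 192.3, 211.6)

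The cost is therefore 1 to 4 sessions out of 108 planned for those affected, plus protocol wording and a small change to device logic. No visits or participants are added. Anyone whose dose after any Table 9 cut is 200 or more is unaffected.
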